Neuropathic Pain After Orchidectomy and Sex Reassignment Surgery (NPASRS)

ClinicalTrials.gov ID NCT 04538170

Date of Initial Ethical Release: 23.10.2013

Correspondence:

[contact]

Department of Anaesthesiology and Intensive Care Medicine, Eberhard-Karls-University, Tuebingen, Germany

Background:

Phantom pain may occur after surgical removal of male reproductive organs. The indication for the surgery determines the physical and psychological predisposition of the patient that may differ between men who receive a tumor orchidectomy and those receiving gender reassignment surgery.

Objective:

To determine whether patients experience phantom pain after gender reassignment surgery.

Study protocol:

Transgender women who had undergone gender reassignment surgery in the Urology Clinic of the University of Tübingen and in the Surgical Clinic Munich-Bogenhausen should be retrospectively surveyed using written questionnaires. There should be at least 6 months between the survey and the surgical intervention for gender reassignment. Participation in the survey is pseudonymized and voluntary.

The control group includes men who had to undergo an orchectomy for oncological indications. Here, too, there should be at least 6 months between the operation and the survey in order to record chronic pain and not postoperative pain.

Study population:

The cohort size of the study is limited in that the gender reassignment surgery is a very rare procedure. We aim to include around 40 women in this group, with an estimated response rate of 80% for the questionnaires, so we want to write to at least 50 women. The control group (patients after oncological indicated orchectomy) should include 145 men based on biometric considerations - with an estimated response rate of 60% in this group, we would write to 242 patients. For a difference of 20% considered relevant for the occurrence of phantom pain (approx. 25% share after oncological indicated orchidectomy, 5% after gender reassignment), a significance level of 5% with a power of 80% could be achieved.

Contact is made via the operating urological departments of the University Clinic Tübingen and the Surgical Clinic Munich-Bogenhausen. For this purpose, the patients are informed about the study (participant information). The questionnaire is pseudonymized and sent by post. Patients are asked to give their consent to the evaluation and publication of the research results in scientific journals. After receipt of the signed declaration of consent, the questionnaire will be scientifically evaluated.

Inclusion and exclusion criteria: Participation in this study is voluntary. You must be of legal age. The women and men should be able to give their consent and be able to fill out the form independently and without outside help.

Test procedure:

Basic questionnaire to collect demographic data such as age, gender

Pain detect questionnaire for the detection of neuropathic pain

Record of phantom feelings and phantom pain through dichotomous questions

Ability to cope with pain recorded by the FESV questionnaire

Numerical rating scale (NRS) for recording the intensity of pain

Health-related quality of life SF 12

Sexual satisfaction through dichotomous questions

Incidence of surgical complications from dichotomous issues

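### Does the Objective need rewriting because it names one group while the study is powered for a comparison with men?

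*Combined protocol and SAP*

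**What the plan says.** The combined document is short and has no separate analysis section. Its Objective is a single sentence about one group: "To determine whether patients experience phantom pain after gender reassignment surgery".

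The other sections are comparative:

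- **Background:** physical and psychological predisposition "may differ between men who receive a tumor orchidectomy and those receiving gender reassignment surgery".
- **Study protocol:** "The control group includes men who had to undergo an orchectomy for oncological indications".
- **Study population:** the sizing begins "For a difference of 20% considered relevant for the occurrence of phantom pain". It assumes about 25% in men and 5% in women, a 5% significance level and 80% power, with 145 men.
- **Study population, on the women:** "We aim to include around 40 women in this group". The reason given is practical: "The cohort size of the study is limited in that the gender reassignment surgery is a very rare procedure".
- **Test procedure:** the outcome is collected as "Record of phantom feelings and phantom pain through dichotomous questions".

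The document names no hypothesis, primary endpoint, test, sidedness, estimator or confidence interval.

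**The concern.** Read literally, the Objective asks a yes/no question about women alone, while the significance level and power belong to a contrast with men. Two consequences seem to follow. The powered question is not stated as an aim, and the stated aim has no target precision.

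If it were unclear which question carries the main conclusion, the emphasis could be chosen after the data are seen. With no cases among 40 women, the literal Objective might be answered with a flat no, although the data would still allow a rate of several per cent. With five cases, the Objective would be answered yes while the comparison with men missed significance. Naming both questions, ranking them and planning an interval for the women's rate looks like a cheap safeguard.

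**Working it through.** **Inputs.** From Study population: 25% (men), 5% (women), significance level 5%, power 80%, 145 men, about 40 women, response rates 60% and 80%. Assumptions, because the document is silent: a two-sided test; Fisher's exact and the uncorrected pooled z test as two common choices; 36/145 men with phantom pain (24.8%, the whole number nearest 25%).

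**1. Does the stated sample size belong to a comparison?** Take the allocation ratio r = 40/145 = 0.2759 and the weighted mean rate p̄ = (0.25 + 0.2759 × 0.05)/1.2759 = 0.2068.

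- Uncorrected number of men: n = [1.96·√((1 + 1/r)·p̄(1 − p̄)) + 0.842·√(0.25·0.75 + 0.05·0.95/r)]² / 0.20² = (1.707 + 0.505)² / 0.04 = 122.3, so 123.
- With continuity correction: n′ = (n/4)·[1 + √(1 + 2(1 + 1/r)/(n·0.20))]² = (122.3/4)·[1 + √1.378]² = 144.5, so 145 men and 145 × 0.2759 = 40 women.
- Mail-outs: 40/0.80 = 50 and 145/0.60 = 241.7, so 242.

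Every figure in the plan is reproduced. Power at 145 and 40 is 80.2% with the correction, 87.9% without it, and 86.7% by two-sided Fisher enumeration. The sizing is a two-group comparison and is sound as such.

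**2. How well do the same data answer the literal Objective?** Exact (Clopper-Pearson) 95% intervals with 40 women:

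| Cases | Rate | 95% CI |
|---|---|---|
| 0 | 0% | 0% to 8.8% |
| 2 | 5% | 0.6% to 16.9% |
| 4 | 10% | 2.8% to 23.7% |
| 5 | 12.5% | 4.2% to 26.8% |

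The upper limit for 0/40 is 1 − 0.025^(1/40) = 8.8%. The Wilson interval for 2/40 is 1.4% to 16.5%, so the choice of method matters little. If the true rate is 5%, the chance of no case is 0.95^40 = 12.9%, and of at least one 87.1%.

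**3. Do the two questions conflict?** Against 36/145 men (difference is men minus women):

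| Women | Difference, points (Newcombe 95% CI) | Fisher p | Pooled z p |
|---|---|---|---|
| 0/40 | 24.8 (14.0 to 32.4) | 0.0001 | 0.0004 |
| 2/40 | 19.8 (6.7 to 28.3) | 0.004 | 0.006 |
| 4/40 | 14.8 (0.3 to 24.6) | 0.051 | 0.044 |
| 5/40 | 12.3 (−2.7 to 22.7) | 0.13 | 0.097 |

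At 0/40, no cases seen and a rate lower than in men point the same way. At 5/40, some women report phantom pain and a difference from men is not shown; both statements can be true at once. They answer different questions and do not contradict each other. Under the planned 5%, five or more cases has probability 4.8%.

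**4. What would rewording alter?** The sample size stays at 145 and 40, the questionnaire is the same, and the intervals above are unchanged.

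**The case for a change.** The strongest case for a change is that intent which can be inferred is not the same as a stated primary question. Nothing in the document ranks the two questions or promises an interval. At a true rate of 5%, about one study in eight (12.9%) would see no case, and a literal yes/no Objective invites that result to be read as absence. Three added sentences would prevent this at almost no cost.

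Part of this stands. The Objective is incomplete as a summary, and a clearer one would name the comparison. It is also true that the test is unnamed, and that at 4/40 against 36/145 Fisher (0.051) and pooled z (0.044) fall on opposite sides of 5%. Ranking the two questions would not settle that, since the verdict there depends on the choice of test and not on the wording of the Objective.

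The rest does not carry. Only one question has a relevant difference, a significance level and a power attached to it, so which one the study was sized for is not in real doubt. Nothing in the document says that zero cases would be reported as proof of absence. The women's precision follows from a stated practical limit, which no wording can relax.

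**Conclusion.** No change to the plan is needed. The Objective is narrower than the design, but the control group, the 20-point relevant difference and the sizing, reproduced exactly at 145 and 40, show the intended comparison. The data also answer the literal Objective, with the precision that about 40 women allow: 0.6% to 16.9% at the planned 5%, and an upper limit of 8.8% if no case is seen.

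Following the plan as written gives a sound proportion and a sound comparison. Adding an interval to each is ordinary reporting practice and requires no new patients, data or design decision. No stated figure is wrong.

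This rests on about 40 women and 145 men responding, on a two-sided comparison (the reading under which the sample size is reproduced with continuity correction), and on 36/145 as the illustrative result in men.

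### Does the 6-month gap before the survey fail to keep resolved postoperative pain out of the phantom-pain answer?

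*Combined protocol and SAP*

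**What the plan says.** Under Study protocol, patients who have had gender reassignment surgery "should be retrospectively surveyed using written questionnaires". The timing rule for them is "There should be at least 6 months between the survey and the surgical intervention for gender reassignment". For the oncological controls the same minimum is repeated with its purpose: "at least 6 months between the operation and the survey in order to record chronic pain and not postoperative pain". The Objective, in the present tense, is to find out if patients experience this pain after gender reassignment surgery.

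Test procedure lists the components of the postal questionnaire in one line each. The outcome appears as "Record of phantom feelings and phantom pain through dichotomous questions". Other yes/no components cover sexual satisfaction and surgical complications ("Incidence of surgical complications from dichotomous issues"). The questionnaire itself is not reproduced.

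Study population bases the sample size on a 20-point difference in phantom pain, with an "approx. 25% share after oncological indicated orchidectomy, 5% after gender reassignment", a 5% significance level, 80% power, about 40 women and 145 men.

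**The concern.** The minimum gap is the only means the protocol states for separating chronic from postoperative pain. It controls who is eligible and when they answer. It does not control how far back the answer reaches. Take a respondent whose phantom pain lasted two months and who is surveyed at 24 months. That person satisfies the timing rule and could truthfully say yes to an item covering the whole time since surgery.

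Three features leave that reading open: the survey is called retrospective, the item has no stated reference period, and the planning rates are described as occurrence without saying whether they are chronic shares. If the item did reach back over the whole period, a group difference could not be read as a difference in chronic pain. If the item and the planning rates used different definitions, the real power would not be the planned 80%.

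**Working it through.** **1. The planned size.** Inputs from Study population: p1 = 0.25 (controls), p2 = 0.05 (women), n1 = 145, n2 = 40, alpha 0.05 (taken as two-sided), power 0.80. Allocation k = 40/145 = 0.2759; 1 + 1/k = 4.625; pooled rate (0.25 + 0.2759 × 0.05)/1.2759 = 0.2068.

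Uncorrected control size:

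m = [1.960 × √(0.2068 × 0.7932 × 4.625) + 0.842 × √(0.25 × 0.75 + 0.05 × 0.95/0.2759)]² / 0.20² = (1.707 + 0.505)² / 0.04 = 122.3.

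With continuity correction:

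n1 = (m/4) × [1 + √(1 + 2 × 4.625/(122.3 × 0.20))]² = 144.5, rounded up to 145, with 40 women.

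The mailing numbers also follow: 40/0.80 = 50, and 145/0.60 = 241.7, rounded up to 242. The plan's figures reproduce.

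**2. Power at 145 against 40.**

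Power = Φ[(d − c − 1.960 × s0)/s1], where d is the difference in rates, c = 0.5 × (1/145 + 1/40) = 0.0159, and s0 and s1 are the pooled and unpooled standard errors.

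At 25% against 5%: (0.20 − 0.0159 − 1.960 × 0.0723)/0.0498 = 0.849, so power is 80.2%. The exact two-sided Fisher test gives 86.7%.

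**3. What a mismatch of definitions could do.** The shares in the first column are assumptions; the documents give none.

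| Assumption | Controls vs women | Corrected | Fisher |
|---|---|---|---|
| Item and rates share one definition | 25% vs 5% | 80.2% | 86.7% |
| Rates any-time, item chronic; 80% of pain persists in both groups | 20% vs 4% | 62.1% | 75.3% |
| Rates chronic, item any-time; resolved pain in 10% of the others, both groups | 32.5% vs 14.5% | 53.4% | 60.9% |
| As above, but 10% in controls and 2% in women | 32.5% vs 6.9% | 93.5% | 95.7% |

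The rates follow directly: 0.8 × 25 = 20 and 0.8 × 5 = 4; 25 + 0.10 × 75 = 32.5; 5 + 0.10 × 95 = 14.5; 5 + 0.02 × 95 = 6.9. Power moves down or up with shares nobody has stated.

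**4. A bound with no assumed share.** If 25% and 5% are any-time shares, the chronic shares lie in 0 to 25% and 0 to 5%, so the chronic difference lies between 0 − 5 = −5 and 25 − 0 = +25 points. This only says that a part lies between nothing and the whole. Its starkest case, 5% against 5%, needs 20/25 = 80% of affected controls and none of the affected women to have recovered. Nothing in the protocol points that way.

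**5. Which period the text favours.**
- The purpose clause says the gap is there to record chronic pain. It achieves that if the item asks about pain at the time of the survey.
- The Objective is in the present tense.
- Calling the survey retrospective can simply mean that patients are approached after surgery already done; it sets no recall window.
- The yes/no format is uninformative. Complications are past events by nature, while sexual satisfaction, in the same format, is most naturally a present state.
- The postoperative pain to be left out is not defined. It may mean ordinary surgical pain, which a phantom-pain item does not ask about.

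**The case for a change.** The strongest case for acting is that the protocol itself treats the chronic/postoperative distinction as important, offers only the gap to secure it, and then drops the distinction where the rates are given. The present tense in the Objective states an aim and does not define an item. The pain detect questionnaire and the numerical rating scale have no stated recall period and are not tied to the yes/no outcome, so they do not close the gap. Stating the period would take a sentence or two.

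Of this, the logic stands: a minimum interval alone cannot set the period an answer covers, and neither the period nor the basis of 25% and 5% is written down. What does not stand is the step from there to a defect. No look-back item is shown, no two statements conflict, and no figure is wrong. Several different periods would all meet the stated aim, so there is no one better method that the plan has passed over.

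**Conclusion.** No change to the plan follows. This is a detail left to the questionnaire, and the protocol's stated purpose already points to the sensible way of filling it: phantom pain present at the survey, asked alike in both groups. On that reading, and with 25% and 5% taken as shares on the same definition, the 6-month rule works and 145 against 40 gives 80.2% power (corrected) or 86.7% (Fisher).

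The conclusion rests on two things the documents cannot confirm: that the form asks about present or otherwise persistent pain, and that the planning rates refer to the same thing. If either fails, the effect could be material, from 53% to 94% corrected power in the illustrations above, but its size and direction depend on shares that are not given. Whoever analyses the data will have the form and can report the period it covers beside the result.

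### The six-month window does not separate pain from the orchidectomy from pain due to later cancer therapy or disease, and no described item lets the painDETECT, NRS and SF-12 comparisons do so

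*Combined protocol and SAP*

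**What the plan says.** The title names neuropathic pain after orchidectomy and sex reassignment surgery. The Objective and the planning figures under Study population (25% against 5%) concern phantom pain.

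- **Controls (Study protocol):** "The control group includes men who had to undergo an orchectomy for oncological indications".
- **Timing, controls (Study protocol):** "at least 6 months between the operation and the survey in order to record chronic pain and not postoperative pain".
- **Timing, women (Study protocol):** "There should be at least 6 months between the survey and the surgical intervention for gender reassignment".
- **Eligibility (Inclusion and exclusion criteria):** voluntary participation, legal age, and "The women and men should be able to give their consent and be able to fill out the form independently and without outside help".
- **Background data (Test procedure):** "Basic questionnaire to collect demographic data such as age, gender".
- **Neuropathic pain and intensity (Test procedure):** "Pain detect questionnaire for the detection of neuropathic pain" and "Numerical rating scale (NRS) for recording the intensity of pain".
- **Phantom pain (Test procedure):** "Record of phantom feelings and phantom pain through dichotomous questions", listed separately from painDETECT.

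The remaining Test procedure lines cover coping with pain (FESV), SF-12, sexual satisfaction and surgical complications. No line mentions chemotherapy, radiotherapy, recurrence or the site of pain. No analysis, stratification or adjustment is described.

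**The concern.** Both groups share one safeguard for linking pain to surgery: six months since the operation. For the women that date may well be enough. For the men, the orchidectomy can be one step in cancer care that continues. Neurotoxic chemotherapy can itself cause neuropathic pain, and radiotherapy or recurrence can cause other pain. A man surveyed after such treatment could score positive on painDETECT, report pain on the NRS, or have a lower SF-12 score, for reasons unrelated to the loss of the testis.

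If so, a between-group difference on these three measures would combine two things: what follows from the operation in its different settings, and what follows from further cancer treatment. With the data as described, nobody could separate them afterwards. This matters because neuropathic pain is the subject of the title and painDETECT is the instrument listed for it.

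**Working it through.** **1. The plan's own figure.** Inputs from Study population: p1 = 0.25, p2 = 0.05, 40 women, 145 men, 5% level, 80% power. Two-sided testing is assumed, since the plan does not state it. With k = 40/145 = 0.276 and pooled rate (0.25 + 0.276×0.05)/1.276 = 0.207:

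- Uncorrected: n = [1.96·√((1+1/k)·0.207·0.793) + 0.842·√(0.25·0.75 + 0.05·0.95/k)]² / 0.20² = 122.3, so 123 men.
- With continuity correction: n = (122.3/4)·[1 + √(1 + 2(1+1/k)/(122.3·0.20))]² = 144.5, so 145 men and 40 women.

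The stated size reproduces, as do the mailings: 40/0.80 = 50 and 145/0.60 = 241.7, rounded up to 242. No figure in the plan is disputed here.

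**2. The text, side by side.** The controls' clock starts at surgery and serves to exclude postoperative pain. It is not linked to the end of treatment or to disease status. Eligibility does not restrict either one. The instrument list describes no variable from which either could be recovered, and no pain-site restriction.

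**3. Possible size.** The documents give neither the share of controls with further therapy (e) nor the share of those made positive by it (s). Both are assumptions: e = 20–50%, s = 10–30%. Affected share q = e×s.

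| | e | s | q | Men of 145 |
|---|---|---|---|---|
| Low | 0.20 | 0.10 | 0.02 | 2.9 |
| High | 0.50 | 0.30 | 0.15 | 21.75 |

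Some of these men would already be positive for other reasons. If a share p is positive anyway, independently of therapy, the observed rate is p + (1−p)q and the added share is (1−p)q. Borrowing p = 25% from the phantom-pain planning rate:

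- Low: 0.75×0.02 = 0.015, or 1.5 points (25% becomes 26.5%).
- High: 0.75×0.15 = 0.1125, or 11.25 points (25% becomes 36.25%).

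**4. Could this produce a difference by itself?** Assume a true rate of 5% in both groups, 145 men and 40 women, and an uncorrected two-sided z-test at 5%, enumerated exactly. The table gives the chance of a significant excess in controls.

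| q | Observed control rate | Spurious difference | Chance |
|---|---|---|---|
| 0 | 5% | 0 | 0.4% |
| 2% | 6.9% | 1.9 points | 3% |
| 5% | 9.75% | 4.75 points | 11% |
| 10% | 14.5% | 9.5 points | 34% |
| 15% | 19.25% | 14.25 points | 64% |

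The low end is minor. From about 5% upward the contamination would matter for a dichotomised painDETECT result. The 5% is also borrowed from phantom pain, so this is an illustration, not an estimate.

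**The case against.** **The study is built on phantom pain.** The Objective, the relevant difference and the power statement all concern it, and it has its own questions. The plan gives painDETECT, NRS and SF-12 no hypothesis, target difference or primary role. This stands, and it limits the point to those three measures.

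**The six-month rule does what it says.** The plan never presents it as the end of cancer treatment. This also stands. The gap is a missing second safeguard, not a faulty rule.

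**The contrast is between indications.** The Background treats the indication as determining the patient's predisposition, and cancer treatment comes with the control indication. This is fair: the plan does not say that differences will be attributed to the operation alone. But a reader of a study of pain after these operations still needs to know how much of a difference comes from later therapy, and the described data cannot show it.

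**Absence is not proven.** The questionnaires are not reproduced, the demographic list is open-ended, and each instrument has one line. A therapy or site item may exist. Only its absence from the description can be asserted.

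**Stronger readings fail.** A reader might infer that the bias mimics an expected finding of less neuropathic pain in women. The plan states no such expectation, because 25% and 5% are phantom-pain rates. A reader might also infer that the error can only run against the controls, with none of the 40 women affected. Only this one source is absent in the women by indication. If the instruments are not site-specific, unrelated pain in the women counts too, and the documents say nothing of their other illnesses. The net direction is therefore unknown.

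**Conclusion.** The concern holds in a limited form. As described, the plan cannot separate pain after orchidectomy from pain due to later cancer therapy or disease in the comparisons on painDETECT, NRS and SF-12. The phantom-pain objective and its sample size are much less exposed and are not called into question.

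The size cannot be found from the documents. Under the assumed ranges, 2–15% of controls would be affected, and the control rate would rise by about 1.5–11 points if 25% were already positive. With no upper limit on time since surgery, the number of men surveyed close to treatment is also unknown. The documents do not say that any control had further therapy, so these figures show what is possible, not what to expect. The case for changing the plan is that the remedy is cheap and the information cannot be recovered from the described data later.

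**What to change.** 1. **For the men, add a short item:** chemotherapy or radiotherapy after the orchidectomy (yes/no), whether it is ongoing, and whether the disease has recurred. If the basic questionnaire already asks this, say so in the plan.
2. **For both groups, add one instruction:** answer painDETECT and the NRS for the operated region (genitals, groin, scar). SF-12 cannot be tied to a site, so it depends on items 1 and 3.
3. **Add one set of table rows:** the between-group differences in painDETECT, NRS and SF-12, with confidence intervals, for all controls and again for men without further cancer treatment. Interpret them by comparing the two estimates. Loss of significance in the smaller subset should not be read as no difference.

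**Cost.** A few lines on a postal form and some extra rows, with no change to sample size or eligibility. The subset intervals are wider. If 20–50% of men are set aside, 116 to about 72 remain. At rates of 25% and 5% (borrowed again), the 95% half-width 1.96·√(0.25·0.75/n + 0.05·0.95/40) goes from 9.8 points with n = 145 to 10.4 with n = 116 and 12.0 with n = 72.5. Men without further treatment may also differ in disease stage, so the subset result is a check on the full comparison and does not replace it.

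### Does the phantom pain comparison fail because the plan does not say which organ the yes/no questions refer to?

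*Combined protocol and SAP*

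**What the plan says.** The Background speaks of the organs in general terms: "Phantom pain may occur after surgical removal of male reproductive organs". The Objective is descriptive and concerns the women: "To determine whether patients experience phantom pain after gender reassignment surgery".

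Under Study protocol, the study group is defined by gender reassignment surgery, with no list of the organs removed, and the controls by a single named operation: "The control group includes men who had to undergo an orchectomy for oncological indications".

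Study population then sizes a comparison of the two groups: "For a difference of 20% considered relevant for the occurrence of phantom pain", with assumed rates of "approx. 25% share after oncological indicated orchidectomy, 5% after gender reassignment". It plans around 40 women and 145 men, and states that "a significance level of 5% with a power of 80% could be achieved".

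The Test procedure section gives the outcome one line: "Record of phantom feelings and phantom pain through dichotomous questions". It does not name an organ or say which item is compared. Neither the 25% nor the 5% is tied to a site.

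**The concern.** A phantom sensation is felt in a part that has been removed, so its frequency depends on what was removed. The controls are defined by orchidectomy alone. If gender reassignment surgery also removes penile tissue (an assumption that the documents neither state nor exclude), an unspecified phantom pain question covers one lost organ in the men and more than one in the women. The percentages for the two groups would then not measure quite the same thing.

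Two features make this look serious. The data come from a postal questionnaire and the plan describes no later contact, so a site that was not asked about would be hard to recover. The women's group is also small: 5% of 40 is two women, and each further positive woman adds 1/40 = 2.5 percentage points. If the outcome were wider than the one behind the 5%, the planned power might not be reached.

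**Working it through.** **1. The plan's own figures.** Inputs from Study population: p_w = 0.05, p_m = 0.25, difference d = 0.20, 5% significance, 80% power, 40 women and 145 men, so r = 145/40 = 3.625. A two-sided test is assumed, because the plan does not state the sidedness.

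- Pooled rate: p̄ = (0.05 + 3.625 × 0.25)/4.625 = 0.2068.
- Uncorrected number of women: n = [1.960·√((r+1)·p̄(1−p̄)) + 0.842·√(r·p_w(1−p_w) + p_m(1−p_m))]² / (r·d²) = (1.7070 + 0.5048)² / (3.625 × 0.04) = 33.74.
- Continuity correction: n_c = (n/4)·[1 + √(1 + 2(r+1)/(n·r·d))]² = (33.74/4)·[1 + √1.3782]² = 39.86 women.
- Men: 39.86 × 3.625 = 144.5.

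Rounded up, these are the stated 40 and 145. The mailing numbers follow too: 40/0.80 = 50 and 145/0.60 = 241.7, so 242.

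Exact power at 40 against 145, by enumerating both binomial distributions, is 87% (Fisher), 89% (uncorrected chi-square) or 82% (continuity-corrected chi-square). The plan names no test, but each of these reaches 80%.

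**2. Which way an extra organ pushes.** Grant the assumption that the women lost an organ the controls kept. Let W_t be the share of women with testicular phantom pain and W_a the share with phantom pain in any removed organ. Everyone counted in W_t is also counted in W_a, so W_a ≥ W_t. For the men, who lost only a testis or testes, any-organ and testicular phantom pain coincide at M. Therefore

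M − W_a ≤ M − W_t.

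The plan expects the women to be lower (5% against 25%). In that direction the any-organ count gives the smaller difference. If the women are lower on any-organ pain, they are at least as far below the men on testicular pain. The distortion cannot create the planned result.

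**3. What it does to power.** Read plainly, the 5% is the share of women with phantom pain of any kind after their operation. The planned comparison then uses the outcome it was sized on and keeps its 82% to 89%. A testis-only comparison would lose nothing: at an assumed testicular rate of 4%, Fisher power is 92% (88% to 94% across the three tests).

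Lower figures need two further suppositions: that the 5% means testis only, and that the any-organ rate is some higher number. At an assumed 7.5%, Fisher power is 69% (63% to 74% across tests). At 10% it is 51% (44% to 56%). The documents give no rate by organ, so these values show only how power depends on the women's rate, whatever the reason for a misjudged rate. They do not measure an effect of leaving the organ unnamed.

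**The case for a change.** The case for a change is that phantom pain carries the whole sample size and yet has one line of definition. None of the other listed instruments is linked to the site of phantom pain. Adding a site item would need one or two tick boxes and a sentence or two, with no change to either group size. A null result, or one with the women higher, would be harder to read if positive answers could come from an organ only the women lost.

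Part of this stands. The plan does not say which item is compared or what the 25% and 5% refer to, and the direction argument protects only a finding that the women are lower. The rest is weaker:

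- The gap is shown in a short synopsis, not in the questionnaire, which may already ask by site.
- The organ mismatch rests on an assumption about the operation that the documents do not state.
- Any phantom pain after each operation is a coherent outcome, and it fits the general wording of the Background. Restricting the comparison to the testis asks a different question, on which reasonable statisticians could differ.
- A testis-only comparison would still leave indication and type of operation confounded, so it would not make the groups like for like.

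**Conclusion.** The concern does not call for a change. The plan leaves the site of phantom pain unwritten, which is a gap in description that analysts can fill by stating which question they compared. Followed as written, the plan answers its Objective with the share of women reporting phantom pain. Its group sizes reproduce at 40 and 145, with exact power of 82% to 89% at the stated rates.

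If the women did lose an additional organ, counting pain in it can only reduce the planned difference of 20 percentage points, so a finding that the women are lower would be conservative. The remaining uncertainty lies in a null or reversed result, and its size cannot be derived from the documents because they give no organ-specific rates.

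This conclusion rests on a two-sided test, on the plain reading of the 5% as any phantom pain after the operation, and on the men having lost only testicular tissue.
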